Low-frequency repetitive transcranial magnetic stimulation (LF-rTMS) of the contralesional hemisphere is a safe procedure that suppresses local cortical activity of the non-affected cerebral cortex (**Li et al, 2016**). The primary motor cortex (M1) forms a main part of the motor cortices and contributes to the high order control of motor recovery of the hemiparetic upper limbs in stroke patients. It was assumed that the induced inhibitory effect of LF-rTMS on the non-lesional hemisphere can cause direct increase in the neural activation of the lesional hemisphere which can consequently regain the cortical interhemispheric balance and eventually can produce functional improvement in post-stroke patients with upper limb hemiparesis (**Blesneag et al,2015, Du et al, 2018**).

Statement of the Problem:

- Is there a significant effect of the contralesional low frequency repetitive transcranial magnetic stimulation (LF-rTMS) on cortical excitability modulation and consequently on the upper limb motor performance in stroke patients?
- The recommended minimum number of contralesional low frequency repetitive transcranial magnetic stimulation (LF-rTMS) sessions that can induce significant cortical excitability changes in relation to the conventional therapeutic physical therapy interventions in stroke patients?
- The recommended maximum number of contralesional low frequency repetitive transcranial magnetic stimulation (LF-rTMS) sessions that can induce significant cortical excitability changes before reaching a plateau in relation to the conventional therapeutic physical therapy interventions in stroke patients?

Purpose of the study:

- To assess and analyze the effect of contralesional low frequency repetitive transcranial magnetic stimulation (LF-rTMS) on cortical excitability and consequently its impact on the upper limb motor performance in stroke patients.
- To determine the recommended minimum and maximum number of contralesional low frequency repetitive transcranial magnetic stimulation sessions (LF-rTMS) in conjunction with the conventional physical therapy rehabilitation program that can induce significant impact on cortical excitability by analyzing the sequential rate of change in cortical excitability in response to contralesional (Lf-rTMS) stimulation in stroke patients.

Significance of the study

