- The selected patients were randomly assigned into two equal groups (control group (GA) and study group (GB)), The randomization was done by random generator using permuted blocks of different sizes(Randomized Controlled Trial).
- All patients were selected with mild to moderate motor impairment verified according to the national istitutes of health stroke scale (NIHSS) (score 1-15) and modified ashworth scale (MAS) (1 or 1+).
- Fugl-Myer upper extremity assessment scale (FMA-UE) and hand grip dynamometer were used to assess the upper limb motor function for each patient in both groups (before and after treatment).
- Single pulse TMS was used to assess cortical excitability represented in measuring the active motor threshold from the contralesional (CAMT) and the ipsilesional (IAMT) primary motor “hot spot” for each patient in both groups (before and after treatment).
- Single pulse TMS was used to assess the sequential change in cortical excitability represented by the sessional measurement of (CAMT) and (IAMT) for all patients in both groups.
- Patients participated in the study were not informed whether they are in the Control group(GA) or in the Study group(GB) (Single blind study).
- The treatment sessions for all patients in both groups was conducted daily, five times per week for two consecutive weeks.
 - The control group (GA) were treated by a conventional physical therapy upper limb rehabilitation protocol (**Lie et al,2015**).

- The study group (GB) were treated with the conventional physical therapy upper limb rehabilitation protocol in addition to the contralesional low frequency repetitive transcranial magnetic stimulation (LF-rTMS).

Limitations:

An Effort was made to minimize the effect of the possible limitations which are:

1. The psycho-physiological status of the patients; all the patients were interested and motivated during all the sessions.
2. The transportation of all patients from the Outpatient clinic, Faculty of Physical Therapy, Cairo University was comfortable and without any effort or extra load on the patient as much as possible.
3. Each patient was assessed using single pulse TMS at the neurophysiology lab at Kasr El Aini, teaching Hospital, Cairo University, at a time suitable for each patient and without any list of waiting as much as possible.

Basic assumption:

It was assumed that:

- The sample of this study were carefully selected to represent all the subacute stroke population.

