- The mean values of the **Sequential rate of change in cAMT and iAMT** findings over the 10 therapeutic sessions were assessed by comparing the CAMT and the IAMT mean values of each session in relation to the previous session findings for each patient in both groups
- **Paired t Test** for independent samples test was used to compare the mean sessional values (sequential change) and the mean difference in the sessional rate of change of the **cortical excitability findings** represented by cAMT and iAMT between group control group (GA) and study group (GB).
- The alpha point of 0.05 was used as a level of statistical significance (when P = 0.05 is usually classed as “significant”, P = 0.01 as “highly significant”, and P = 0.001 as “very highly significant”) (**Betty and Jonathan, 2003**).

- All statistical calculations were done using computer program IBM SPSS (Statistical Package for the Social Science; IBM Corp, Armonk, NY, USA) release 22 for Microsoft Windows.

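### Sequential change is planned as steps from the previous session, with no reference named for session 1; each session's change from the pre-treatment threshold should also be compared between arms

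*Combined protocol and SAP*

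**What the plan says.** Purpose of the study makes the recommended minimum and maximum number of sessions an aim, to be reached by analysing the sequential rate of change in cortical excitability.

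Delimitations describes two uses of single-pulse TMS in separate bullets. One measures cAMT and iAMT before and after treatment in both groups. The other is to "assess the sequential change in cortical excitability represented by the sessional measurement of (CAMT) and (IAMT) for all patients in both groups". Sessions are "conducted daily, five times per week for two consecutive weeks".

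B- Inferential statistics then gives three relevant analyses:

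- The post-to-pretreatment change in cAMT and iAMT is compared between groups.
- The sequential rate of change over the ten sessions is taken from mean cAMT and iAMT at "each session in relation to the previous session findings for each patient in both groups".
- A between-group test is used to "compare the mean sessional values (sequential change) and the mean difference in the sessional rate of change" in cAMT and iAMT.

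The document does not say whether a sessional reading is taken before or after that day's stimulation, what session 1 is compared with, or whether the pre- and post-treatment readings belong to the sequential series.

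**The concern.** A step from the previous session asks whether this session added anything to the last one. That suits a search for a plateau. The minimum number of sessions is a different question: after how many sessions can the change from the starting threshold be told apart from control? No planned analysis measures each session's change from the pre-treatment value.

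The step series also has an open end. If readings follow stimulation and session 1 has no earlier reference, any first-session change is already inside the first value of the series. The steps then cannot show a minimum of one session, and a response concentrated early would look flatter than it is.

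The between-group comparison of sessional means does include session 1. However, those means carry whatever difference in starting threshold the two small arms happen to have.

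**Working it through.** **Inputs.** Sessions: five per week for two weeks (Delimitations). Series: ten sessions, each against the previous one (B- Inferential statistics). Patients: forty in two equal groups, so 20 per arm (Delimitations). Reading time within a session: not stated, so both cases are taken.

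**Reproducing the plan's figure.** 5 × 2 = 10 sessions, which matches the stated 10.

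**Counting steps.** Index each reading by the number of sessions completed when it is taken. Ten post-session readings have indices 1 to 10; ten pre-session readings have indices 0 to 9. The pre-treatment value has index 0 and the post-treatment value index 10. A step covers a session only if the index rises by one.

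| Readings used | Sessional readings after stimulation | Sessional readings before stimulation |
|---|---|---|
| Ten sessional only | 9 steps, session 1 missing | 9 steps, session 10 missing |
| Plus pre-treatment | 10 steps, none missing | 9 steps, session 10 missing |
| Plus post-treatment | 9 steps, session 1 missing | 10 steps, none missing |
| Plus both | 10 steps, none missing | 10 steps, none missing |

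In the last row there are 12 readings if all are distinct, hence 11 differences. One of the 11 joins two readings with the same index and contains no session. It is the first difference if readings precede stimulation, and the last if they follow it.

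**How much one missing step could matter.** The documents give no response curve, so these are illustrations.

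- Linear response: each step is 1/10 = 10% of the total.
- Assumed exponential approach with a half-life of h sessions:
  - share of session 1 = (1 − 2^(−1/h)) / (1 − 2^(−10/h))
  - share of session 10 = (2^(−9/h) − 2^(−10/h)) / (1 − 2^(−10/h))

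| h (assumed) | Session 1 share | Session 10 share |
|---|---|---|
| 1 | 50% | 0.1% |
| 2 | 30% | 1.3% |
| 3 | 23% | 2.9% |
| 5 | 17% | 5.0% |

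**Steps against change from session 0.** With a linear response, every step is 10% of the total, while the change from session 0 after k sessions is k × 10%. Each single step can be too small to detect while the accumulated change is clear, so the accumulated change is the quantity that bears on the minimum.

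**Chance imbalance in raw sessional means.** With between-patient SD σ and 20 per arm, the difference in pre-treatment means has standard deviation σ√(1/20 + 1/20) = σ√0.1 = 0.32σ by chance alone. To the extent that thresholds are stable within a patient, that difference carries into every sessional comparison.

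**The case against.** A reader might infer that one session's effect is always lost and that the plan discards the pre- and post-treatment readings. The documents do not support that. Both thresholds are recorded before and after treatment in every patient, and the table shows that they can supply all ten steps under either timing. The wording about each of ten sessions is compatible with an analyst using the pre-treatment value as the first reference. It is even possible that the pre-treatment reading is the session 1 reading, or that thresholds are taken on both sides of stimulation. The text settles none of this.

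Nor are the steps the only sessional analysis. Comparing raw sessional means between randomised arms includes session 1. If readings follow stimulation, that comparison is an unbiased estimate of the first-session effect, so a one-session minimum could show there. This stands. The weakness is chance imbalance in small arms, not bias, and the plan names the rate of change, not the raw means, as the basis for the session number.

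The harm also depends on an unstated fact. With pre-session readings the missing step is the last, which bears little on the minimum. The larger shares need both post-session readings and an assumed curve. This too stands.

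Finally, adding both end readings without care creates an interval with no session in it, and noise there could be credited to session 1 or session 10. That is a reason to index the readings, not a reason to leave the pre-treatment value out.

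**Conclusion.** The point holds as a weakness in the analysis as written, not as an unavoidable loss of data. Sequential change is defined as steps from the previous session, session 1 has no named reference, and sessional means are compared without regard to the pre-treatment threshold. Used alone, the ten sessional readings give nine steps, and which session drops out depends on a timing that the plan does not give. For the minimum number of sessions, which is a stated aim, that series is poorly suited.

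The size of the loss is unknown from the documents. The range of 0.1% to 50% rests on assumed half-lives and on both possible timings, and should not be read as an estimate.

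The gain from taking the starting level out also rests on an assumption. With equal variances and correlation ρ between the pre-treatment and session values, a change score has variance 2σ²(1 − ρ), against σ² for the raw value. It is therefore more precise when ρ exceeds 0.5. The documents do not give ρ.

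**What to change.** In B- Inferential statistics, revise the text on sequential change as follows:

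1. Take the pre-treatment cAMT and iAMT as session 0, and compare each session's change from session 0 between the two arms. Report this alongside the previous-session steps.
2. State whether sessional readings are taken before or after stimulation, and at what corresponding point in control sessions. Index each reading by the number of sessions completed.
3. If readings precede stimulation, let the post-treatment value close session 10. Whatever the timing, do not count an interval with no stimulation in it as a session effect.
4. Say which result informs the minimum number of sessions (change from session 0) and which informs the plateau (the steps).

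With this indexing all ten sessions are covered under either timing. The cost is a few sentences. The thresholds are already measured in both arms, so no visit or measurement is added.

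### The sequential rate of change is left undefined, and whether the session-to-session steps are averaged or tested one by one, it is not a sound basis for finding the minimum or maximum number of sessions.

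*Combined protocol and SAP*

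**What the plan says.** Under Purpose of the study, the second aim is to determine the minimum and maximum number of sessions "by analyzing the sequential rate of change in cortical excitability". The Statement of the Problem describes the maximum as the number of sessions "that can induce significant cortical excitability changes before reaching a plateau". Treatment is "conducted daily, five times per week for two consecutive weeks", which gives 10 sessions. Under Delimitations, both motor thresholds (contralesional and ipsilesional) are to be measured at each session in both groups, as well as before and after treatment.

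Under Data Analysis and Statistical Design, B- Inferential statistics, the sequential rate of change is obtained by "comparing the CAMT and the IAMT mean values of each session in relation to the previous session findings for each patient in both groups". The next bullet names a t test that "was used to compare the mean sessional values (sequential change") and, in the same sentence, "the mean difference in the sessional rate of change" between the two groups.

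Three things are not stated: whether the change is an absolute difference, a percentage or a ratio; whether the mean is taken over sessions within a patient or over patients at each step; and whether the first value is session 1 or a separate pre-treatment reading.

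**The concern.** Onset and plateau are questions about timing. The measure named to answer them is built from steps between neighbouring sessions. Averaging such steps over the course removes the timing. Testing them one at a time keeps the timing, but puts each test on a small, noisy difference that shares a reading with its neighbour. In the first case a recommended number of sessions would rest on a statistic that does not contain the answer. In the second it could rest on chance variation between sessions. Because the text allows both interpretations, two analysts following it could also report different statistics.

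**Working it through.** The plan gives no sample-size, power or effect-size figure for this analysis, so there is no figure to reproduce.

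**Inputs from the document.** There are 10 sessions (5 per week for 2 weeks), hence 9 steps if session 1 is the first value. There are 40 patients in two equal groups, so 20 per group. Alpha is 0.05; sidedness is not stated and two-sided is assumed. There are two outcomes, one per hemisphere.

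**Assumptions (not in the document).** Readings S1 to S10 have within-patient SD 1 and errors that are either independent or AR(1) with correlation ρ. Where an effect is needed, the group difference reaches 1 SD by session 10.

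**Interpretation A: steps averaged over sessions.**

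(1/9) × [(S2 − S1) + (S3 − S2) + … + (S10 − S9)] = (S10 − S1)/9

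With a separate pre-treatment reading S0 as the first value, the result is (S10 − S0)/10. Four made-up courses from 60 to 51 show the consequence:

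| Course | Mean absolute step | Mean percentage step | Mean log-ratio step |
|---|---|---|---|
| Steady change | −1.0 | −1.79% | −0.01806 |
| Plateau from session 4 | −1.0 | −1.76% | −0.01806 |
| No change until after session 7 | −1.0 | −1.76% | −0.01806 |
| Overshoot and return | −1.0 | −1.63% | −0.01806 |

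Absolute and log-ratio steps cancel exactly. Percentage steps do not, but they still give the early-plateau and late-onset courses the same value. None of these averages locates onset or plateau.

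**Interpretation B: each step tested between groups.**

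- *Shared readings.* The steps S(k) − S(k−1) and S(k+1) − S(k) contain S(k) with opposite signs. With AR(1) errors each step has variance 2(1 − ρ) and neighbouring steps have covariance −(1 − ρ)², so their correlation is −(1 − ρ)/2. That is −0.5 at ρ = 0, −0.25 at ρ = 0.5 and −0.05 at ρ = 0.9.
- *False steps.* If the nine tests were independent, the chance of at least one false positive would be 1 − 0.95⁹ = 0.370. Simulation that keeps the shared readings (20 per group, independent errors, no true effect) gives about 0.34 per hemisphere. For both hemispheres, the independence formula gives 1 − 0.95¹⁸ = 0.603, as a rough guide only.
- *Apparent reversal.* In the same null setting, a significant step is followed by one of opposite sign about 90% of the time, against about 67% for neighbouring steps in general. The following step is itself significant in the opposite direction only about 18% of the time.
- *Power of one step.* A linear difference reaching 1 SD gives 1/9 SD per step. The standardised difference is λ = (1/9) / √[2(1 − ρ) × 2/20]. At ρ = 0, λ = 0.111/0.447 = 0.25, and Φ(λ − 1.96) + Φ(−λ − 1.96) is about 6%. Simulation gives 5–6%. At ρ = 0.9, λ = 0.111/0.141 = 0.79 and power is about 12%.

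**Does a slope over all readings gain power over the mean step?** Only sometimes (simulated; 20 per group; difference of 1 SD at session 10):

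| Course of the difference | ρ | Mean step | Slope on all readings |
|---|---|---|---|
| Linear | 0 | 58% | 87% |
| Linear | 0.5 | 59% | 65% |
| Linear | 0.9 | 80% | 80% |
| Levels off at session 4 | 0.5 | 59% | 57% |

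**The case against.** The strongest reply is that the plan compares two things in that sentence, not one. The comparison of mean sessional values uses sessions 2 to 9 directly and can show when the groups separate. A reader might infer from the cancellation that the plan as a whole throws away the intermediate sessions. The document does not support that, and this part of the reply stands in full. What it leaves open is that these are, as written, group-against-group t tests with no model of the course over sessions. Purpose of the study also ties the aim to the rate of change rather than to these values.

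A second reply is that the cancellation depends on one interpretation. That also stands: a group mean at each step fits the wording at least as well and does not cancel, and percentage steps cancel only approximately. The cancellation is therefore a conditional finding. The alternative interpretation meets the difficulties under B instead.

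A reader might also infer that a longitudinal analysis would raise power from 58% to 87%. Those figures need independent errors and a linear difference. The gain is small at moderate correlation, absent at high correlation, and slightly reversed when the difference levels off early, which is the situation the trial asks about. Nor does power for a slope answer a question about onset or plateau.

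Finally, an opposite-signed step after a significant one looks like a reversal, not a plateau. Noise can imitate onset followed by reversal; that it imitates onset followed by a plateau has not been shown.

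**Conclusion.** The concern holds in conditional form. The rate-of-change measure is undefined, and neither plausible definition can soundly locate onset or levelling. Averaged absolute or log-ratio steps reduce exactly to an end-minus-start change; this is algebra and rests on no assumption about the data. Averaged percentage steps do not cancel exactly but still carry no usable timing. Separately tested steps carry about a 34% chance of at least one false step in nine per hemisphere, and about 6% power per step for a linear difference reaching 1 SD. Both figures assume independent errors, and the power figure also assumes the effect size. Higher serial correlation weakens the link between neighbouring steps and raises single-step power for that linear course to about 12% at ρ = 0.9.

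The finding does not extend to a claim that sessions 2 to 9 go unused, or to any general loss of power. It should be corrected because a stated purpose of the trial rests on this measure and the remedy uses readings already planned.

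**What to change.** For each hemisphere, replace the step-based comparisons and the separate sessional t tests with one linear mixed model. Fit it to the pre-treatment reading and all sessional readings from all 40 patients, with group, session (categorical) and group-by-session as fixed effects, a patient effect, and serially correlated residuals. State whether the pre-treatment reading is distinct from the session 1 reading. Then, in order:

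1. Test group-by-session overall.
2. Report the GB − GA difference in change from pre-treatment at each session with multiplicity-adjusted confidence intervals, and judge onset from these. State whether the adjustment also spans the two hemispheres.
3. Judge levelling from one contrast fixed in advance, for example the group difference in mean change over the later sessions against the middle sessions, with the sessions in each set named. Report it with its confidence interval. A non-significant contrast alone should not be read as a plateau.

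If a rate of change is still reported descriptively, define it as absolute or percentage and say what the mean is taken over.

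The cost is revised SAP wording and some extra analysis, with no new data or visits. The downside is that a covariance structure must be assumed, so the plan should name it and a fallback. The revision should not promise a gain in power.
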